#### 4. TRIAL POPULATION

Trial Population: This trial will consist of up to 300 adults (21 years of age or older) undergoing trans-jugular liver biopsy with HVPG measurement at TJU or at HUP.

Subjects eligible for trial enrollment will be identified by the co-investigators, [name] (at TJU) and [name] (at HUP) from their patient population of subjects scheduled for a trans-jugular liver biopsy. The research coordinators for this study will explain the study to the patients at the respective clinical sites. The patient will be given time to consider the risks and benefits of the study and ask questions about participation. The coordinator will review the consent form with the patient and then the patient will be given the form to review. The patient, coordinator, and a study investigator will all sign the consent form. The patient will be given a copy of the signed consent form for their records.

#### 4.1 Inclusion Criteria

All subjects accepted for this trial must fulfill all the following criteria:

- Be scheduled for trans-jugular liver biopsy the day of the ultrasound procedure.
- Be at least 21 years of age.
- Be medically stable.
- If a female of child-bearing potential, must have a negative pregnancy test.
- Be conscious and able to comply with study procedures.
- Have read and signed the IRB-approved Informed Consent form for participating in the study.

#### 4.2 Exclusion Criteria

Subjects who fulfill any of the following conditions or who have had the following procedures will be excluded from this trial:

- Females who are pregnant or nursing.
- Patients not scheduled for trans-jugular liver biopsy
- Patients who have received an investigational drug in the 30 days before study drug administration, or will receive one within 72 h afterwards.,
- Patients with known or suspected right-to-left, bi-directional, or transient right-to-left cardiac shunts
- Patients with pulmonary hypertension or unstable cardiopulmonary conditions
- Patients currently on chemotherapy or with other primary cancers requiring systemic or hepatic loco-regional treatment.
- Patients who are medically unstable, patients who are seriously or terminally ill, and patients whose clinical course is unpredictable. For example:
  - Patients on life support or in a critical care unit.
  - Patients with unstable occlusive disease (e.g., crescendo angina)
  - Patients with clinically unstable cardiac arrhythmias, such as recurrent ventricular tachycardia.
  - Patients with uncontrolled congestive heart failure (NYHA Class IV)
  - Patients with recent cerebral hemorrhage.
  - Patients who have undergone surgery within 24 hours prior to the study sonographic examination.
- Patients with a history of anaphylactic allergy to eggs or egg products, manifested by one or more

of the following symptoms: generalized urticaria, difficulty in breathing, swelling of the mouth and throat, hypotension, or shock. (Subjects with nonanaphylactic allergies to eggs or egg products may be enrolled in the study, but must be watched carefully for 1 h following the administration of SONAZOID).

- Patients with congenital heart defects.
- Patients with severe emphysema, pulmonary vasculitis, or a history of pulmonary emboli.
- Patients with respiratory distress syndrome
- Patients with thrombosis within the hepatic, portal, or mesenteric veins.

[figure not shown]
Subject identification will be maintained with a study specific alphanumeric code including the institution (TJU or HUP), patient number (001 and onwards at both the sites) and the patient's initials.

## 5. MEDICATIONS

Sonazoid will be provided by GEHC (Oslo, Norway). An FDA Sponsor-Investigator IND application will be submitted to the FDA and studies will not commence until regulatory approval has been obtained from the FDA as well as the IRB committee for TJU and HUP.

Sonazoid is a sterile non-pyrogenic suspension of microspheres of lipid stabilized perfluorobutane (PFB) for contrast-enhancement, with a median diameter between 2.4 and 3.5  $\mu\text{m}$  and less than 0.1 % larger than 7  $\mu\text{m}$ . Sonazoid is formulated as a powder for injection consisting of lyophilized sucrose entrapping hydrogenated egg phosphatidyl serine (HEPS) PFB microspheres under a PFB headspace. Each milliliter of Sonazoid contains roughly 1.2 billion microspheres.

Sonazoid is supplied as a dry powder within 10 ml sealed vials. The headspace of the vials contains PFB. Three vials with 48  $\mu\text{l}$  of Sonazoid microbubbles (6 ml) will be prepared for each subject by resuspending each vial in 2 ml of injection grade water supplied by GEHC, as described in Appendix B. Infusions will be performed as described in the Instructions for Use protocol supplement provided by GEHC (Appendix B). All materials and supplies used for the infusion procedure will be identical to those described in GE Healthcare's current Sonazoid IND. A diagram of this infusion setup is shown below in Figure 1.

**Figure 1:** Setup used for Sonazoid infusion for all patients during SHAPE imaging. This setup is discussed briefly in section 5 and in detail in the attached GEHC provided infusion protocol (Appendix B).

Briefly, a 20-22 gauge cannula will be placed in a vein in the subject's right or left arm. A 0.9%NaCl solution will be started and used to fill up the connecting tubes before being connected to a 3-way stopcock. The stopcock will then be connected to the extension tubing leading to the cannula. All three

vials of suspended Sonazoid will be drawn into a 10 ml syringe, placed in a syringe pump at the same level or below the patient, and connected directly to the stopcock. After the stopcock has been opened, the NaCl solution will be infused at a rate of at least 2 ml/min, and Sonazoid will be infused at the desired rate of 0.024  $\mu$ l/kg body weight/minute (suspension infusion rate of 0.18 ml/kg/hour), but may be reduced if necessary to achieve optimal levels of contrast. This infusion rate was selected based on our group's previous experiences with Sonazoid infusion in human subjects in general [Halpern et al. 2002; Landmark et al. 2008] and in SHAPE portal hypertension subjects in particular [Eisenbrey et al. 2013]. This dosing scheme is designed to avoid (or limit) the number of cases that has to be discarded due to insignificant enhancement in the hepatic veins (as in our pilot study; Eisenbrey et al. 2013). This dosage is based on GEHC's previous experience of dosing Sonazoid by infusion. The maximum amount of microbubbles infused over 15 minutes (0.36  $\mu$ l/kg) is well below the maximal tested dose which was still found safe in Phase I clinical trials (2.7  $\mu$ l of microbubbles/kg in PBI 0001 as detailed in the Sonazoid Investigator's Brochure).

Sonazoid will be stored in a secure cabinet, with only the study investigators and research personnel having access. New vials must be prepared for each subject's contrast administration. Unused drug and empty vials will be properly disposed of after reconciling in the log of study drug.

### 5.1 Contraindications

Sonazoid should not be administered to patients with known or suspected hypersensitivity to egg phosphatidyl serine. Patients with a history of anaphylactic allergy to eggs or egg products will be excluded from the study.

The safety of ultrasound contrast agents in patients with cardiac shunts has recently been called into question. Therefore, patients with known or suspected right-to-left, bi-directional, or transient right-to-left cardiac shunts will be excluded from this study.

The safety of Sonazoid in patients with 1) severe emphysema, pulmonary vasculitis or a history of pulmonary emboli; and 2) respiratory distress syndrome has not been studied. Therefore, patients with any of these conditions will be excluded from participation. Additional exclusion criteria are listed in section 4.2.

#### 5.2 Randomization

This is a non-randomized trial; therefore, no randomization procedure is required.

#### 5.3 Blinding and Unblinding Methods

This is an open-label trial; therefore, no blinding or unblinding procedures for the trial drug are required.

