**Trial Procedures:** Subjects eligible for trial enrollment will be identified by the co-investigators, [name] (at TJU) and [name] (at HUP) from their patient population of subjects scheduled for a trans-jugular liver biopsy. The research coordinators for this study will explain the study to the patients at the respective clinical sites. The patient will be given time to consider the risks and benefits of the study and ask questions about participation. The coordinator will review the consent form with the patient and then the patient will be given the form to review. The patient, coordinator, and a study investigator will all sign the consent form. The patient will be given a copy of the signed consent form for their records.

After consenting to participate in this study, a full demographic profile, known drug allergies or intolerances, and review of the subject's medical/surgical history will be recorded. Patients with known cardiac shunts will be excluded from the study. If the subject is a woman of childbearing potential, she will have a urine pregnancy test (the results of which will be made available to the subject prior to study initiation).

Whenever a subject undergoes a trans-jugular liver biopsy with transcatheter free and wedged hepatic venous pressure measurements as part of their standard clinical care and agrees to participate in the study, we will perform the corresponding SHAPE measurement within the 3 hours of post-recovery observation to ease transportation for patients and ensure that hydration status and other variables, which could potentially affect portal pressures, are equivalent. Administration of Sonazoid will be performed under

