direct supervision of a medical doctor. Additionally, resuscitation equipment will be in immediate proximity to the patient during Sonazoid infusion. Three vials (6 ml) of Sonazoid microbubbles (16  $\mu$ l per vial when reconstituted) will be prepared for each subject by resuspending each vial in 2 ml of water for injection, supplied by GEHC, as described in the instructions provided by GEHC (Appendix B). Infusions will be performed as described in Appendix B. All materials and supplies used for the infusion procedure will be identical to those described in GE Healthcare's current Sonazoid IND. Briefly, anintravenous cannula will be placed in a vein in the subject's arm. A 0.9% NaCl solution will be started and used to fill up the connecting tubes before being connected to a 3-way stopcock. The stopcock will then be connected to the extension tubing leading to the cannula. All three vials of suspended Sonazoid will be drawn into a 10 ml syringe, placed in a syringe pump at the same level or below the patient, and connected directly to the stopcock. After the stopcock to the 0.9% NaCl solution has been opened, the saline solution will be infused at a rate of at least 2 ml/min. Then, Sonazoid will be co-infused at the target rate of 0.024  $\mu$ l/kg body weight/minute (suspension infusion rate of 0.18 ml/kg/hour), but the rate may be reduced if necessary to achieve optimal levels of contrast. This infusion rate was selected based on our group's previous experiences with Sonazoid infusion in human subjects in general [Halpern et al. 2002; Landmark et al. 2008] and in SHAPE portal hypertension subjects in particular [Eisenbrey et al. 2013]. This dosing scheme is designed to avoid (or limit) the number of cases that has to be discarded due to insignificant enhancement in the hepatic veins (as in our pilot study; Eisenbrey et al. 2013). The dosage is based off the GEHC provided, study specific resuspension and infusion instructions (Appendix B) and the total Sonazoid dose given over a maximum of 15 minutes (0.36  $\mu$ l/kg) will be well below the maximal tested dose which was still found safe in Phase I clinical trials (2.7  $\mu$ l of microbubbles/kg in PBI 0001 as detailed in the Sonazoid Investigator's Brochure). The duration of contrast agent infusion will range from 5 to 10 minutes.

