After beginning the contrast infusion, a modified Logiq 9 scanner (GE Healthcare) with a broad bandwidth curvi-linear array (model 4C) will be used to obtain RF data (for SHAPE measurements) within the hepatic and portal veins. Both the experimental machine and software will be labeled as an

investigational device with a GRC provided label prior to beginning any clinical experiments (21 CFR 812.5). Once the infusion of Sonazoid has started, ultrasound imaging will be performed with the 4C curved linear array to guide SHAPE ROI placement into the portal vein (while also visualizing a hepatic vein). The SHAPE optimization algorithm will be activated ([Dave et al. 2013]) and the acoustic power will be adjusted to produce the maximum change in subharmonic amplitudes (i.e., maximizing the sensitivity of SHAPE). Then the ROI will be increased to visualize the hepatic and the portal veins, and the corresponding subharmonic data will be acquired at the optimal acoustic power setting in 5 s segments during the infusion of the Sonazoid suspension. Ultrasound imaging will be performed at a transmit frequency of 2.5 MHz and the subharmonic obtained at 1.25 MHz. All measurements will be repeated three times. The depths, sizes, and locations of the portal and hepatic veins will be determined by the sonographer and saved in a reference image.

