### 3.1 Trial Duration

Individual participation in this trial will be limited to ultrasound imaging studies within the two hour period following a trans-jugular liver biopsy (during which their hepatic wedge pressure will be measured

with a pressure catheter as part of the standard of care at TJU and HUP). Patients are monitored for two hours (1 hour post Sonazoid injection). The entire ultrasound imaging protocol will require approximately one hour. Subjects identified in the initial examination as having portal hypertension (by HVPG results) will be monitored by SHAPE for up to 18 months. These subjects typically have surveillance CT or MRI scans every 6 months to check for liver cancer and at those times a repeat SHAPE examination will be performed. Any repeat trans-jugular biopsies performed in this population will also trigger a repeat SHAPE study. Moreover, these patients will have a complete blood test every 3 months and these clinical variables (platelets, albumin, MELD, etc.) as well as any medication will be recorded. Finally, most subjects with portal hypertension will undergo an endoscopy examination every 1 to 2 years [de Franchis 2005; Merkel et al. 2004]. Results of any concomitant imaging study or procedure (including endoscopies) will be noted. The end point for this part of the study will be any one new complication (e.g., liver cancer) or a marked worsening in any complication (e.g., MELD scores), liver transplantation, death, or the end of this clinical trial (after 3 years). On an average, these patients will be monitored three times during the course of this clinical trial. The time to reach the end point will be noted if a new complication or a marked worsening in any complication occurs.

Subject recruitment is expected to last 3 years (April, 2014 – January, 2017). This includes monitoring disease progression and/or treatment response. Analysis and publication of results are expected to take an additional 2 months (January– March, 2017). Volunteer Registry Database forms will be submitted to the National Institute of Health’s Office of Regulatory Compliance and Quality at the completion of the research study.

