### 6.3.2 Ultrasound Imaging

The ultrasound examinations will be performed by a qualified sonographer. Procedures and equipment for this trial will be used in accordance with typical clinical procedures. All trial procedures will be conducted in accordance with Good Clinical Practice. A modified Logiq 9 scanner (GE Healthcare, Milwaukee, WI) with a broad bandwidth curvi-linear array will be used in to obtain RF data (for SHAPE measurements) within the hepatic and portal veins. Both the experimental machine and software will be labeled as an investigational device with a GE provided label prior to beginning any clinical experiments (21 CFR 812.5). Ultrasound imaging will be performed at a transmit frequency of 2.5 MHz and the subharmonic obtained at 1.25 MHz. Using this setup, acoustic pressure amplitudes will all be below 1.21 MPa peak negative pressure, 2.19 MPa peak positive pressure. The SHAPE algorithm will be activated and the acoustic power will be adjusted to produce the maximum change in subharmonic amplitudes (i.e., maximizing the sensitivity of SHAPE). Subharmonic data from the microbubbles (i.e., SHAPE) will be acquired in 5 s segments during the infusion of the Sonazoid suspension. All measurements will be repeated three times.

During the examination, the subharmonic pressure estimates will be displayed on the Logiq 9 scanner, these estimates will be noted and the data will be stored on a PC. Data will be compared to the

transcatheter portal pressure measurements, which comprise the free and wedged hepatic venous pressure (FHVP and WHVP, respectively) and the hepatic vein pressure gradient (HVPG; measured as the difference between the WHVP and FHVP), which are acquired as part of standard of care for all patients undergoing trans-jugular liver biopsy at TJU and HUP.

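### The plan does not provide for keeping the SHAPE operator or data processor unaware of the catheter HVPG, which is measured first, so knowledge of it could inflate accuracy and correlation

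*Combined protocol and SAP*

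**What the plan says.** **Blinding.** Section 5.3 notes that the trial is open-label and that "no blinding or unblinding procedures for the trial drug are required". No other section of the protocol text deals with masking.

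**Order of the tests.** HVPG is obtained at the transjugular biopsy. The Synopsis then says "we will perform the corresponding SHAPE measurement within the 3 hours of post-recovery observation". Section 3.1 places the scan differently, as "ultrasound imaging studies within the two hour period following a trans-jugular liver biopsy". The two windows should be reconciled, but in both the reference value exists before the baseline scan starts.

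**Operator choices.** The Synopsis describes imaging "to guide SHAPE ROI placement into the portal vein" and adds: "The depths, sizes, and locations of the portal and hepatic veins will be determined by the sonographer". For the contrast infusion, "the rate may be reduced if necessary to achieve optimal levels of contrast". Acoustic power is set with the SHAPE optimization algorithm: "the acoustic power will be adjusted to produce the maximum change in subharmonic amplitudes".

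**Feedback and repeats.** Under section 6.3.2 the pressure estimates appear on the scanner during the examination, and "these estimates will be noted and the data will be stored on a PC". Every measurement is made three times. No rule is given for averaging, choosing or rejecting readings. The Synopsis and sections 5 and 6.2 mention that pilot cases were discarded for poor hepatic-vein enhancement, but the plan gives no criterion for discarding cases here.

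**Data.** Section 7.2.2 describes one database holding both HVPG and SHAPE results, with no stated order of entry or separation of access.

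**Follow-up.** Section 3 selects patients for repeat SHAPE by their baseline HVPG.

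**The concern.** This is a diagnostic accuracy study with catheter HVPG as the reference standard. Being open-label for the contrast agent matters little. What matters is whether the index test is acquired and read without knowledge of the reference. If the person placing the region of interest, or deciding which segment or repeat to use, knows the HVPG and sees a live pressure estimate, choices can move toward the known value without any intent. This is review bias, and it acts in the favourable direction.

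The quantities at stake are the ones the trial exists to estimate: sensitivity 89% and specificity 81% at HVPG of 10 mmHg or more (H1), a correlation of 0.82 (H2), and a correlation above 0.90 with repeat HVPG (H3). The Synopsis aims to establish the accuracy of SHAPE conclusively, and a bias of this kind would not show in the confidence intervals.

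**Working it through.** **1. The plan's precision figure, and whether masking enters it.** For a correlation of 0.82, section 7.2.3 gives 264 patients for a 95% interval of width 0.08 and 343 for width 0.07. With Fisher's z, the limits are tanh(atanh(0.82) ± 1.96/√(N − 3)).
- N = 264: 0.776 to 0.856, width 0.080.
- N = 343: 0.782 to 0.852, width 0.070.
- N = 300 (the chosen size): atanh(0.82) = 1.157 and 1.96/√297 = 0.114, giving 0.779 to 0.854.

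The plan's figures reproduce. The interval covers sampling error only, so masking changes neither N nor the width, and a larger N would not remove a masking bias.

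**2. Keeping the repeat nearest HVPG.** The plan does not describe this practice, but it does not exclude it either. The inputs are assumptions: a single-read correlation of 0.70, with a share f = 0.30 or 0.50 of the error variance arising between repeats. Set the HVPG variance to 1. The error variance is then 1/0.70² − 1 = 1.041.

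The mean of three reads has r = 1/√(1 + 1.041 × [(1 − f) + f/3]).
- f = 0.30: 1/√(1 + 1.041 × 0.80) = 0.74.
- f = 0.50: 1/√(1 + 1.041 × 0.667) = 0.77.

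Simulation then replaces the mean by the nearest read in some or all patients:

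| Patients in whom the nearest read is kept | r, f = 0.30 | r, f = 0.50 | Sensitivity and specificity at a median cut |
|---|---|---|---|
| None | 0.74 | 0.77 | 0.76 / 0.78 (f = 0.30 / 0.50) |
| 20% | 0.76 | 0.79 | up about 1.6 points |
| 25% | 0.76 | 0.79 | up about 2 points |
| All | 0.84 | 0.88 | 0.84 / 0.86 (f = 0.30 / 0.50) |

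The rise in r is about 0.02 at 20 to 25% of patients and about 0.11 at 100%.

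**3. A second model, as a check on direction.** Let recorded SHAPE = (1 − k) × true SHAPE + k × HVPG on a standardised scale, with k assumed. Then r′ = [(1 − k)r + k] / √[(1 − k)² + k² + 2k(1 − k)r].
- True r = 0.75, k = 0.10: 0.775/√0.955 = 0.793.
- True r = 0.75, k = 0.20: 0.834.
- True r = 0.70, k = 0.10 and 0.20: 0.751 and 0.799.

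Reaching the hypothesised 0.82 would need k of about 0.24 from a true 0.70, 0.17 from 0.75, or 0.10 from 0.78. Both models move correlation and accuracy upward. Neither shows how large the drift would be in this trial.

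**The case against.** The strongest reply is that the plan's silence is not evidence of exposure. Section 5.3 speaks only of the drug. The catheter measurement belongs to interventional radiology and the scan to a qualified sonographer, and no section says that the sonographer is told the HVPG. This stands. A reader might infer that the operator is in fact unmasked and that the results will be inflated. The documents support only that nothing prevents either.

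A second reply is that operator freedom is limited. Acoustic power follows an algorithm with a stated criterion, the permitted rate reduction is tied to contrast level rather than to the pressure estimate, and vein depth and size are anatomical. This narrows the routes. It leaves region placement, choice of segment, use of the repeats and rejection of scans.

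Third, a reader might infer that the harm could never be undone. That goes too far. RF data are obtained, examinations are recorded, data are stored and a reference image is saved, so segment choice and processing could be re-read masked. Only live acquisition choices could not be repeated.

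Fourth, the 0.11 rise assumes that the nearest read is kept in every patient, and that SHAPE and HVPG share a scale on which nearness can be judged. The plan relates them by regression and takes its cut-off from the ROC curve afterwards, so the operator has no preset SHAPE cut-off to aim at. That figure is therefore the upper end of one mechanism and not an expected effect.

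Finally, most follow-up scans accompany CT or MRI surveillance with no concurrent HVPG to drift toward. The baseline order also protects the HVPG reading from knowledge of SHAPE. Both points stand.

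**Conclusion.** The concern holds as an omission with a known direction and an unknown size. Catheter HVPG precedes the baseline SHAPE exam, SHAPE acquisition and handling involve judgement with live feedback, and the plan has no provision to mask the operator or processor. H1 to H3 are therefore open to review bias if the value reaches them.

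The illustrative range for the correlation is about +0.02 to +0.11. It rests on the assumed single-read correlation of 0.70, the assumed 30 to 50% share of error variance between repeats, and the assumed fraction of patients affected (20 to 25%, or all). If the HVPG never reaches the scanning or processing team, this bias does not arise. The sample size and its stated precision stand. For H3, only scans paired with a repeat HVPG are directly exposed.

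**What to change.** Amend sections 5.3 and 6.3.2 as follows.
- The sonographer, and anyone who chooses regions, segments or processing settings or rejects scans, stays unaware of FHVP, WHVP and HVPG until that exam's SHAPE values are locked in the database.
- All three repeats are used by a fixed rule, for example their mean, and the criterion for rejecting a scan is set in advance and applied masked.
- HVPG is entered separately, by the team that measures it, and linked after the lock.
- Any unmasking is recorded, so that a sensitivity analysis can leave those exams out.
- At follow-up, masking covers the numeric baseline HVPG and any repeat HVPG. It cannot hide the presence of portal hypertension, because cohort membership reveals it.

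For exams already done without masking, a masked re-read of the stored RF data would check segment choice and processing, though not live acquisition.

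The cost is protocol wording and an order of data entry, with no added procedure, visit or patients. The downside is that HVPG must be withheld from the scanning team for a few hours. The documents do not describe how the value is now passed on, so each site would need to confirm that this is workable.
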